## A . OBJECT

Menstrual disorders are one of the most common clinical symptoms in women. Since puberty, about 70% of women have experienced menstrual disorders, including early, delayed, shortened, prolonged, and more importantly oligomenorrhea, amenorrhea, and decreased menstrual flow. At present, the main method of western medicine for the treatment of menstrual disorders is hormone replacement therapy, but the incidence of adverse reactions is high, and the clinical effect is mediocre. Traditional Chinese medicine in my country mostly adopts holistic conditioning therapy for the treatment of irregular menstruation.

Zhenqi Buxue Oral Liquid consists of sheep placenta, pearl, red ginseng, wolfberry, astragalus, angelica, coix seed, ginger and jujube. The excipients are protein sugar and sodium benzoate. Nourishes qi and blood. It is suitable for dizziness, pale complexion, fatigue, lack of energy and lazy words caused by insufficient qi and blood. This study will conduct a comprehensive and in-depth study on its treatment of mental and psychological stress and menstrual disorders with "oligomenorrhea, amenorrhea, amenorrhea and decreased menstrual flow" as the main manifestations. The molecular mechanism and clinical improvement, and the safety and adverse reactions of its use will be clarified.

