## B. STUDY METHOD AND DESIGN

- 330 women with menstrual disorders were observed in a prospective multi-center randomized controlled clinical trial.
- Inclusion Criteria:
  - 1) Aged between 25 and 40 years old;
  - 2) Patients with oligomenorrhea or oligomenorrhea or menopause within three months (see Appendix 1: Diagnostic Criteria of Traditional Chinese and Western Medicine)
  - 3) Meet the clinical medication conditions for progesterone to regulate menstruation
  - 4) The research subjects were informed and voluntarily participated in this study, and signed the informed consent at the same time.
- Exclusion Criteria:
  - 1) Age <25 years or >40 years old, pregnant or breastfeeding women
  - 2) Ovarian dysfunction caused by local ovarian surgery, radiotherapy and

chemotherapy for previous malignant tumors, taking hormones or immunosuppressive drugs;

- 3) Combined with serious or unstable physical diseases that may affect the efficacy of drugs and the conduct of trials, including liver, kidney, gastrointestinal, cardiovascular, respiratory, endocrine, neurological, immune or blood system diseases, etc., mental patients .
- 4) Those who were allergic to the drugs used in the trial or had serious adverse reactions in the past;
- 5) Breast cancer or family history of breast cancer in first-degree relatives, irregular vaginal bleeding, uterine fibroids ( $\geq 3$ cm), endometriosis, atypical endometrial hyperplasia, endometrial cancer and other hormone-dependent reproduction Systemic diseases and other malignant tumors;
- 6) Those with a history of thromboembolic disease or thrombosis;
- 7) Participated in a clinical trial of another research drug within 3 months prior to inclusion in this study (the first interview);
- 8) Those who have used related drugs in the past 3 months or have abused or depended on substances (alcohol or drugs) in the past 3 months; heavy smokers (smokers who smoke 20 or more cigarettes per day);
- 9) Those who met the inclusion criteria, did not follow the doctor's advice, were unable to judge the curative effect or were unable to evaluate the curative effect due to incomplete data.

➤ Methods: The participants were divided randomly into 3 groups:

- 1) Experimental group1(Zhenqi Buxue Oral Liquid): Zhenqi Buxue Oral Liquid, 10 ml each time, 2 times a day for 3 menstrual cycles, orally

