- 2) Experimental group2(Zhenqi Buxue Oral Liquid and Progesterone Capsules): Zhenqi Buxue Oral Liquid was taken orally, 10 ml at a time, twice a day for 3 menstrual cycles + orally from the second half of menstrual cycle, Progesterone Capsules 200mg, once a day for 10 days for 3 menstrual cycles
- 3) Active Comparator group (Progesterone Capsules): Progesterone Capsules 200mg, qd\*10 days\*3 menstrual cycles, orally

- Treatment Period: 3 month.
- Outcomes Measurement:
  - 1) Primary Outcome: Menstrual improvement in women including cycle period, menstrual volume, number of days with bleeding or spotting, monthly rates of amenorrhea
  - 2) Secondary Outcome:
    - a) Sex hormone levels: mainly FSH, LH, E2 and AMH
    - b) AFC: Changes in AFC in pelvic ultrasonography
    - c) SF-36: The change of the MOS item short from health survey
  - 3) Safety Assessment: Adverse reactions, Hepatic Function, Renal Function, Blood Glucose, Breast Ultrasound

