**D. STATISTICS ANALYSIS**

Data was analyzed using SPSS Version 25. All quantitative information are expressed as mean values  $\pm$  standard deviation (SD). Statistical significance was assessed using unpaired Student's t-test or chi-square test. Probability values of less than 0.05 were considered significant and an asterisk identifies such significance in the figures. We will also compare the adverse effect of each group using descriptive statistics.

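### Four primary measures and three groups are each tested at p<0.05 with no lead measure, lead contrast or multiplicity control; if any one significant measure counts, the false-positive chance is about 17–32% (8 tests) or 22–41% (12 tests).

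*Combined protocol and SAP*

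**What the plan says.** Section B states: "330 women with menstrual disorders were observed in a prospective multi-center randomized controlled clinical trial". It continues: "The participants were divided randomly into 3 groups". These are the oral liquid alone (group 1), the oral liquid plus progesterone (group 2), and progesterone alone, labelled as the active comparator (group 3). The allocation ratio is not given.

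The primary outcome is menstrual improvement, "including cycle period, menstrual volume, number of days with bleeding or spotting, monthly rates of amenorrhea". That makes four measures under one heading. No lead measure is named, and no rule combines them. The secondary outcomes begin with "Sex hormone levels: mainly FSH, LH, E2 and AMH", followed by antral follicle count and SF-36.

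Section C records menstrual condition and a symptom score at the follow-ups in months 1, 2 and 3, and asks for a judgement of drug effectiveness at month 3. It does not call any of these the primary endpoint or the primary time point.

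Section D is the whole analysis plan. On tests it says: "Statistical significance was assessed using unpaired Student's t-test or chi-square test". On the threshold it says: "Probability values of less than 0.05 were considered significant and an asterisk identifies such significance in the figures". Neither section D nor any other section gives a lead contrast, an order of testing, an overall three-group comparison or a multiplicity adjustment.

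**The concern.** An unpaired t-test compares two groups, so three groups mean at least two tests for each continuous measure, and there are four primary measures. Each test carries its own 5% error, and nothing limits the total. Because no measure or contrast is named as decisive, a claim for the oral liquid, alone or added to progesterone, could rest on whichever comparison came out significant. The four measures can also disagree, and the plan does not say what the conclusion would then be. The decision rule of the trial is at stake: a reader of the final paper could not tell a planned primary result from the best of several.

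**Working it through.** **No figure to reproduce.** The only error rate in the documents is the per-test threshold of 0.05. The sample size of 330 comes without an effect size, SD, event rate, power or dropout rate.

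**Inputs from the documents.** Four primary measures and three groups (section B), 330 women (section B), threshold 0.05 per test (section D).

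**Assumptions.**
- Equal allocation, 330/3 = 110 per group.
- Two-sided tests, so 2.5% in the direction of benefit.
- No true difference on any measure.
- Normal measures with one common correlation ρ, taken from 0 to 0.9 because the documents give none.
- One pairwise test per measure and contrast.
- Any one significant measure counts as success.

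**Number of tests.** Both experimental groups against progesterone: 4 × 2 = 8. All three pairs: 4 × 3 = 12.

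**Upper check, all tests independent.**
- 8 tests: 1 − 0.95^8 = 33.7%.
- 12 tests: 1 − 0.95^12 = 46.0%.
- 8 tests, benefit only: 1 − 0.975^8 = 18.3%.

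The tests are not independent. Contrasts that share a group correlate 0.5 under equal allocation, and the measures correlate with each other, so the real figures are lower.

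**Simulation.** For each measure, draw standardised group means X1, X2 and X3 with correlation ρ between measures. Form each contrast as (Xj − Xk)/√2 and count a result as significant when its absolute value exceeds 1.96. With 2,000,000 draws per correlation (a separate 100,000-replicate run at individual level, with 110 per group and t-tests on 218 df, agrees to within about half a percentage point):

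| Chance of at least one | ρ = 0 | 0.5 | 0.8 | 0.9 |
|---|---|---|---|---|
| False positive, 8 tests | 31.6% | 26.8% | 20.0% | 16.6% |
| False positive, 12 tests | 40.6% | 34.4% | 25.8% | 21.6% |
| False benefit over progesterone, 8 tests | 17.0% | 13.5% | 10.0% | 8.3% |

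The last row assumes one beneficial direction per measure. It counts only the 8 comparisons with group 3, so adding the third pair does not change it. The benchmark is 2.5% for one two-sided test.

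**Other readings, none of them stated in the plan.**
- One composite endpoint (the case ρ = 1): any false positive 9.1% with two comparisons or 12.2% with three pairs; false benefit over progesterone 4.5%.
- All four measures must improve significantly: false benefit over progesterone 0.0%, 0.2%, 1.0% and 1.8% at ρ = 0, 0.5, 0.8 and 0.9.

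Testing each follow-up separately would add tests and raise the rates in the table.

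**The case against.** The strongest reply is that the plan names a single outcome, menstrual improvement, and that the four items only describe it. If they were combined into one endpoint, false benefit would be about 4.5%; if all four had to improve, it would be under 2%. This stands as a limit on the figures: the 8–17% holds only if any one measure suffices. It does not remove the gap, because no section defines a composite or an all-four rule. The symptom scores and the month-3 effectiveness judgement in section C do not supply one either.

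A second reply is that progesterone is plainly the reference group. The label supports that, and the 8-test row allows for it. It still leaves two experimental groups with no order between them.

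Two stronger readings should be resisted.
- A reader might infer that no direction of benefit is set at all, because section A speaks of "menstrual disorders, including early, delayed, shortened, prolonged, and more importantly oligomenorrhea, amenorrhea, and decreased menstrual flow". That sentence is general background. The next paragraph of section A narrows this study to infrequent or absent periods and reduced flow, and the inclusion criteria also centre on infrequent or absent periods. Benefit can therefore be inferred as a shorter cycle, more volume and less amenorrhea. Only bleeding or spotting days remains ambiguous.
- A reader might infer from the past tense in section D that the groups have already been compared. The same section says "We will also compare the adverse effect of each group using descriptive statistics", so the documents do not settle this.

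**Conclusion.** The point holds as an unspecified decision rule with an inflated error rate. If any one significant primary measure counts as success, the chance of a false-positive primary result is about 17–32% with 8 tests and 22–41% with 12. The chance of a false claim of benefit over progesterone is about 8–17%, against 2.5% for one test. The low end of each range is correlation 0.9 and the high end is correlation 0. All of them rest on equal groups of 110, two-sided tests, equally correlated normal measures and no true effect.

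The documents do not support quoting any one of these as the trial's error rate, since the plan fixes neither the number of tests nor the rule for success. A composite or all-four rule would give much less false benefit, but the protocol would have to say so. The gap concerns the primary outcome and should be closed before any comparison by group.

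**What to change.** Before any comparison by group, name one primary variable with its time point and direction of benefit. Test it at two-sided 0.05 in a fixed order of contrasts. One example is group 2 against group 3, which isolates the oral liquid because both groups receive progesterone, and then group 1 against group 3 only if the first is significant. The sponsor may choose another order if it is fixed in advance. With no true effects this sequence holds the primary error at 5%.

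Make the other three measures secondary. Label secondary results exploratory, or adjust them by Holm if claims are wanted. Say whether the chi-square test is pairwise or overall, and report differences with 95% confidence intervals.

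If comparisons by group have already been made, report every primary measure and contrast with Holm across all of them, and call none pre-specified.

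The cost is wording and no extra patients. Fewer results can be called significant, and the second contrast cannot be claimed if the first fails. For a roughly normal variable, the lead contrast has 80% power for a standardised difference of about 0.38 with 110 analysed per group, or about 0.425 with 88 (20% loss assumed). Under the after-the-fact Holm route, the strictest step over 12 tests (0.05/12 = 0.0042) needs about 0.50 with 110 per group.

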## **E. QUALITY CONTROL MEASUREMENT AND RESULT PUBLICATION**

1. Every center of the research possesses the competence of scientific research to conduct clinical studies. Special people from each center will be put in charge of the research and monitoring the whole procedure. The rights and interests, responsibility and obligation of all centers will be standardized with the research agreement.
2. The maintenance, secrecy and safety of data and informations will be guaranteed by Department of Obstetrics and Gynecology, Peking Union Medical College Hospital.
3. Every center is responsible to subject enrollment and finish the prospective follow up.
4. The researchers' findings will be released in a paper published online.

## **F. SOURCE(S) OF FUNDING**

1. This study does not charge any fee to any patients.
2. All the investigational drugs and cost of the study are provided by Qian Jin Pharmaceutical CO., LTD.
